7.2.3 Secondary endpoint analyses

The responder secondary endpoints (percentage change from baseline $< -5.0\%$ and $< -10.0\%$ in body weight at Week 46, respectively) will be summarised descriptively.

Logistic regression with treatment group and gender as factors and baseline body weight as a continuous linear covariate will be used to estimate the odds ratio for each active BI 456906 dose compared with placebo, and to provide covariate-adjusted estimates of the proportion of responders at each BI 456906 dose.

The analyses of the responder endpoints will be aligned with the treatment policy and hypothetical strategy approaches respectively in [Section 7.2.2](#) for handling early treatment discontinuation and missing data. As a first step, multiple imputation will be performed on the underlying continuous endpoint to generate multiple imputed datasets, each one containing complete data for every patient. A minimum of 100 imputed datasets will be used for this purpose. The imputation model will assume that a patient with missing data follows a similar trajectory to a patient without missing data in the same treatment group (with similar baseline covariates and observed values). The responder endpoints will be derived from the complete data in each of the imputed datasets, and then analysed using the logistic regression model specified above. Finally, the estimates from the logistic regression model will be combined across the imputed datasets in a way which correctly accounts for the within and between imputation variance. Further technical details of the multiple imputation will be provided in the TSAP.

Continuous secondary endpoints measured repeatedly over time will be summarised descriptively and analysed using an MMRM similar to the one specified in Section 7.2.2, except that baseline body weight will be replaced in the model by the baseline value of the relevant endpoint. The model will be used to obtain covariate-adjusted mean estimates of differences between active BI 456906 doses and placebo at the relevant time point.

MCPMod dose finding analyses will not be performed for any secondary endpoints.

7.2.5 Safety analyses

Adverse events will be coded using the Medical Dictionary for Drug Regulatory Activities (MedDRA). Standard BI summary tables and listings will be produced. All adverse events with an onset between start of treatment and end of the residual effect period (REP), a period of 28 days after the last dose of trial medication, will be assigned to the on-treatment period for evaluation.

Safety analyses will be performed on the Treated Set (TS), using the actual maintenance treatment received. Key safety analyses will also be performed using the randomised maintenance treatment (if this is different for any patient).

In general, safety analyses will be descriptive in nature and will be based on BI standards. No hypothesis testing is planned.

Statistical analysis and reporting of adverse events will concentrate on treatment-emergent adverse events, i.e. all adverse events occurring between start of treatment and end of the REP.

Frequency, severity, and causal relationship of adverse events will be tabulated by system organ class and preferred term after coding according to the current version of the Medical Dictionary for Drug Regulatory Activities (MedDRA) at database lock.

The adjudicated events specified in [Section 5.2.6.1.5](#) will be summarised descriptively for each treatment group.

Laboratory data will be analysed both quantitatively as well as qualitatively. The latter will be done via comparison of laboratory data to their reference ranges. Values outside the reference range as well as values defined as clinically relevant will be summarised. Treatment groups will be compared descriptively with regard to distribution parameters as well as with regard to frequency and percentage of patients with abnormal values or clinically relevant abnormal values.

Vital signs, physical examinations and 12-lead ECG observed at screening, baseline, during the course of the trial and at the end-of-trial evaluation will be assessed with regard to possible changes compared to findings before start of treatment.

7.2.6 Other Analyses

Not applicable.

7.2.7 Interim Analyses

Data Monitoring Committee

A Data Monitoring Committee (DMC) will be implemented, with tasks as described in [Section 8.7](#).

Interim Analysis

One interim analysis will be performed after approximately two-thirds of randomised patients have reached Week 20.

The interim analysis will be performed for Sponsor internal phase III planning purposes. The interim analysis results are not intended to be used to stop the trial, nor to make confirmatory claims. No statistical adjustments to Type I error are therefore considered necessary.

The interim analysis will be performed by the Sponsor, using the steps below to protect the integrity of the trial. The external DMC will be informed of the results of the interim analysis and will be given opportunity to review them at the scheduled DMC meeting following their availability.

The interim analysis will be performed by an independent statistics and programming team within BI. Personnel involved with trial conduct at study sites will not have access to unblinded data from the interim analysis. Secure folders with restricted access will be used for the storage of unblinded interim data and results. Further operational details of who will perform the interim analysis, and the steps to be taken to protect the integrity of the ongoing trial, will be specified in a Logistics Plan. Details of the BI personnel who will have access to unblinded interim data or results, and how interim results will be communicated within BI, will be specified in an Access Plan. These documents will be finalised prior to unblinding treatments at interim database lock.

7.3 HANDLING OF MISSING DATA

Every effort will be made to keep the patient in the trial and taking study treatment, where possible. If the patient discontinues from treatment early, every effort will also be made to capture body weight post-discontinuation up to and including Week 46. These data will be used in the treatment policy strategy for handling early treatment discontinuation in the analysis (see [Section 7.2.2](#) for details, including regarding the reason for early treatment discontinuation). Nevertheless, there may still be some missing data, even using such a treatment policy strategy for analysis. In the hypothetical strategy for handling early treatment discontinuation, body weight values recorded after early discontinuation of treatment will not be used and will be handled as if these data were missing.

In both cases, missing data will be handled implicitly by the statistical model (MMRM). This makes the assumption that the data are missing at random (MAR). Patients who do not have a

Week 46 body weight value, but who have earlier post-baseline values, still contribute to this analysis.

For the responder endpoints (percentage change from baseline $< -5.0\%$ and $< -10.0\%$ at Week 46, respectively), analyses will be performed in which the handling of data after early treatment discontinuation and missing data are aligned with the treatment policy and hypothetical strategy approaches for the underlying continuous endpoint of percentage change from baseline at Week 46. This will be done by performing the multiple imputation analysis which was specified in [Section 7.2.3](#). Since the imputation model assumes that a patient who discontinues treatment early behaves in the same way as a similar patient who completed treatment in the same treatment group, this also makes the MAR assumption.

Handling of missing data for other secondary and further endpoints will be specified in the TSAP. In general, unless specified otherwise, MMRM will be used to analyse continuous endpoints, and therefore the MAR assumption is made.

7.4 RANDOMISATION

BI will arrange for the randomisation and the packaging and labelling of trial medication. The randomisation list(s) will be generated using a validated system, which involves a pseudo-random number generator so that the resulting treatment will be both reproducible and non-predictable. The block size will be documented in the Clinical Trial Report (CTR). Access to the codes will be controlled and documented.

Patients will be randomised in blocks using equal allocations to one of 5 double-blind treatment groups. Randomisation will be performed at the start of the dose escalation period at Day 1, Visit 2 (starting dose and timing of dose escalation as outlined in [Table 4.1.4: 1](#)), with allocation to one of the following target maintenance period treatments:

- Placebo once weekly
- BI 456906 0.6 mg once weekly
- BI 456906 2.4 mg once weekly
- BI 456906 3.6 mg once weekly
- BI 456906 4.8 mg once weekly

Randomisation will be stratified by gender. It is anticipated that no more than 70% women will be randomised.

7.5 DETERMINATION OF SAMPLE SIZE

Sample size evaluation was performed using simulation in R software (version 3.6.1), with 10000 simulations performed for each scenario summarised below.

The sample size calculation was based on the following assumptions:

- An overall significance level of 2.5% (one-sided) for the contrast test of the null hypothesis of flat dose response
- The (monotone) dose response shapes specified in [Section 7.2.2](#)
- A placebo effect size (mean percentage change from baseline in body weight at Week 46) of zero
- A maximum effect size (mean percentage change from baseline in body weight at Week 46) in the highest dose group of -10.0%
- A standard deviation of 7.0% [[R20-0479](#)].

Simulations were also performed to investigate departures from the assumed true maximum effect stated above, as well as for different scenarios for the true nature of the dose response relationship. The probability of success for each of these scenarios is summarised in [Table 7.5: 1](#) below.

A success was defined as meeting all 3 of the following criteria:

1. Null hypothesis of flat dose response was rejected in favour of at least one of the alternative candidate models, and
2. A target dose was selected within the dose range using the following criterion: difference in mean between selected dose and placebo < -9.0%, and
3. Proportion of patients in the highest dose group meeting the responder definition (percentage change in body weight from baseline < -10.0%) was greater than 35%.

Table 7.5: 1 Probability of success with N=70 patients in each treatment group and SD = 7.0%.

| | Probability of success (%) | | | | | | |
|-------------------------|----------------------------|-------------|-------------|--------------------|--------------------|---------------------|-------------|
| | | Linear | Exponential | E _{max} 1 | E _{max} 2 | SigE _{max} | AVERAGE |
| True maximum effect (%) | -9.0 | 48.9 | 48.9 | 48.8 | 49.0 | 65.3 | 52.2 |
| | -9.5 | 67.8 | 68.3 | 69.1 | 67.9 | 79.2 | 70.5 |
| | -10.0 | 82.8 | 83.3 | 83.8 | 83.3 | 89.0 | 84.4 |
| | -10.5 | 92.4 | 92.6 | 93.2 | 92.2 | 95.6 | 93.2 |
| | -11.0 | 97.1 | 97.3 | 97.8 | 96.5 | 98.4 | 97.4 |

A sample size of 70 patients per treatment group gives a probability of success of greater than 80% for all assumed dose response shapes, with the assumed maximum dose effect and standard deviation as stated earlier.

Further simulations were performed to investigate the sensitivity of the probability of a successful trial outcome (as presented in [Table 7.5: 1](#)) to different possible allocation ratios which might be observed in practice in an analysis which uses actual maintenance dose. It is possible that some patients may not be able to reach the BI 456906 maintenance dose they

were randomised to according to the planned titration steps in [Section 4.1.4](#), and will receive a lower maintenance dose instead. The scenarios investigated consider the possibility of tolerability issues for patients randomized to the highest BI 456906 dose only, and tolerability issues for patients randomized to one of the top two BI 456906 doses.

All other assumptions other than the allocation ratio are unchanged from what is presented in [Table 7.5: 1](#). For each scenario, 10000 simulations were again used. For simplicity, only the average probability of a successful outcome across the different assumptions on functional form (linear, exponential etc.) is presented in [Table 7.5: 2](#) below. The notation “X-X-X-X-X” is used to refer (from left to right) to the number of patients who received maintenance doses of 0 mg (Placebo), 0.6 mg, 2.4 mg, 3.6 mg and 4.8 mg respectively.

Table 7.5: 2 Probability of success for unequal allocation scenarios in an analysis of actual maintenance dose

| Average probability of successful trial outcome (%) | | | | | | |
|---|-------------------------|------|------|-------|-------|-------|
| Unequal Allocation ratio | True maximum effect (%) | | | | | |
| | | -9.0 | -9.5 | -10.0 | -10.5 | -11.0 |
| | 70-70-70-80-60 | 52.0 | 69.4 | 83.5 | 92.4 | 97.2 |
| | 70-70-70-90-50 | 51.7 | 68.7 | 82.7 | 91.8 | 96.6 |
| | 70-70-80-80-50 | 51.5 | 68.6 | 82.4 | 91.6 | 96.7 |
| | 70-70-90-60-60 | 51.6 | 69.7 | 83.7 | 92.4 | 97.0 |
| | 70-70-100-60-50 | 52.0 | 68.6 | 82.2 | 91.3 | 96.6 |

The average probability of success remained above 80% for the assumed maximum dose effect for all unequal allocation scenarios investigated.

8. INFORMED CONSENT, TRIAL RECORDS, DATA PROTECTION, PUBLICATION POLICY, AND ADMINISTRATIVE STRUCTURE

The trial will be carried out in compliance with the protocol, the ethical principles laid down in the Declaration of Helsinki, in accordance with the ICH Harmonized Guideline for Good Clinical Practice (GCP), relevant BI Standard Operating Procedures (SOPs), the EU directive 2001/20/EC / EU regulation 536/2014 and other relevant regulations. Investigators and site staff must adhere to these principles. Deviation from the protocol, the principles of ICH GCP or applicable regulations as will be treated as “protocol deviation”. Standard medical care (prophylactic, diagnostic and therapeutic procedures) remains the responsibility of the treating physician of the patient.

The investigator will inform the sponsor immediately of any urgent safety measures taken to protect the trial patients against any immediate hazard, as well as of any serious breaches of the protocol or of ICH GCP.

The Boehringer Ingelheim transparency and publication policy can be found on the following web page: trials.boehringer-ingelheim.com. The rights of the investigator and of the sponsor with regard to publication of the results of this trial are described in the investigator contract. As a rule, no trial results should be published prior to finalisation of the Clinical Trial Report.

The certificate of insurance cover is made available to the investigator and the patients, and stored in the ISF.

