2.1 MAIN OBJECTIVES, PRIMARY AND SECONDARY ENDPOINTS

2.1.1 Main objectives

This trial will characterize the dose response curve for BI 456906 in patients with BMI ≥ 27 kg/m² (without diabetes) by assessing 4 doses and placebo. The response is defined as the percentage change from baseline in body weight at Week 46.

The main trial objectives are to demonstrate a non-flat dose response curve, to evaluate the size of the treatment effect (using the difference in mean percentage change between BI 456906 and placebo at Week 46), and to characterise the dose-response relationship.

The primary treatment comparison will be randomised, without regard to whether patients discontinued treatment early (and whether they subsequently received any permitted anti-obesity treatments), or whether patients started the maintenance period with a lower dose than the dose that they were randomised to.

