PoCC will be established if at least one model is statistically significant, rejecting the null hypothesis of a flat dose response relationship for percentage change in body weight jointly over the candidate dose response models, with a contrast test controlled for the family-wise type I error rate at one sided $\alpha = 2.5\%$.

If PoCC is established, the statistically significant (best fitting) model(s) from the above candidate set will be refitted to the data to generate new estimates for all model parameters from the data. The target dose(s) will be estimated from the best fitting model(s) by incorporating information on the minimum clinically relevant effect and accounting for safety.

The primary analysis of percentage change from baseline in body weight at Week 46 will be performed using the FAS and will assign patients to the randomised maintenance dose. It will include all available data without regard to whether patients started the maintenance period

with a lower dose than the one randomised to. For patients who discontinued treatment early, a distinction will be made according to whether this is due to a COVID-19 pandemic-related reason or not. Patients who discontinued treatment early due to a pandemic-related reason (e.g. direct COVID-19 infection, drug supply issue, site closure, quarantine preventing site access) will have data handled after discontinuation as if they were missing. Patients who discontinued treatment early for any other reason will have all available data included after discontinuation, irrespective of whether such patients subsequently received any permitted anti-obesity treatments.

The above approach to the primary analysis specifies a hypothetical strategy for the intercurrent event of pandemic-related early treatment discontinuation, and a treatment policy strategy for the intercurrent event of non-pandemic-related early treatment discontinuation.

The primary endpoint will be summarised descriptively overall, and by pre-specified subgroups (to be specified in the TSAP, but which may include e.g. subgroups based on gender, baseline BMI and age at screening).

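### Does the step-down check in Protocol 7.5, run only by actual dose, leave the success probability of the randomised-dose primary analysis overstated?

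*Protocol*

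**What the plan says.** Protocol 7.5 sets the planning value as "A maximum effect size (mean percentage change from baseline in body weight at Week 46) in the highest dose group of -10.0"%, with placebo at zero, an SD of 7.0% and 70 patients per group. Success needs three things: rejection of the flat curve, a target dose ("A target dose was selected within the dose range using the following criterion": fitted difference from placebo below -9.0%), and more than 35% responders in the top group. Table 7.5:1 gives an average of 84.4% over the five shapes.

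The section then looks at step-down. Some patients may not reach their randomised dose "and will receive a lower maintenance dose instead", and the simulations examine "different possible allocation ratios which might be observed in practice in an analysis which uses actual maintenance dose". One set of scenarios covers "tolerability issues for patients randomized to the highest BI 456906 dose only"; the other covers the top two doses. Table 7.5:2 prints 82.2% to 83.7% at -10%, and its title names the analysis by actual maintenance dose. The section closes: "The average probability of success remained above 80% for the assumed maximum dose effect for all unequal allocation scenarios investigated".

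The primary analysis is different. Protocol 7.2.2 says that it "will be performed using the FAS and will assign patients to the randomised maintenance dose". Protocol 2.1.1 makes the comparison without regard to "whether patients started the maintenance period with a lower dose than the dose that they were randomised to". SAP 7.4.1 likewise uses planned maintenance treatment.

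**The concern.** The text introduces Table 7.5:2 as a sensitivity check on the probabilities in Table 7.5:1, so a reader may take the 80% statement as cover for the primary result. In an actual-dose analysis, step-down changes only the group sizes, and each group keeps its full on-dose mean. In the randomised-dose analysis the sizes stay at 70, and step-down can pull the 4.8 mg arm towards the 3.6 mg mean. That is a different and potentially larger effect.

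The 9-point target-dose criterion is at stake. SAP 7.4.1 applies the same 9% rule in the primary analysis and, if no dose in the range meets it, concludes that no target dose was identified. Section 7.5 also does not say whether -10.0% is the mean of everyone randomised to 4.8 mg or of those who take 4.8 mg.

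**Working it through.** **Inputs.** Means, SD, group size, one-sided 2.5% and the success criteria are from Protocol 7.5. Shapes are from Protocol 7.2.2 and SAP 7.4.1, and model choice by smallest AIC from SAP 7.4.1. The first two rows of Table 7.5:2 imply 70 - 60 = 10 and 70 - 50 = 20 moves from 4.8 to 3.6 mg. The response of stepped-down patients is not in the documents and is an assumption here.

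**Reproducing the plan.** An MCPMod simulation gives the contrasts of SAP Table 7.4.1:1 to three decimals. Averages over the five shapes:

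- Table 7.5:1 at -9.0/-9.5/-10.0/-10.5/-11.0: 51.8/70.1/84.4/93.2/97.4 (printed 52.2/70.5/84.4/93.2/97.4).
- Table 7.5:2 at -10.0, row by row: 83.5/82.3/82.4/83.2/82.2 (printed 83.5/82.7/82.4/83.7/82.2).

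The printed figures are right for the analysis they name.

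**Mean at 3.6 mg when 4.8 mg gives -10.**

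- Linear: -10 × 3.6/4.8 = -7.50.
- Exponential: -5.00 by definition.
- Emax1: ED50 = 4.8 × 0.1/0.9 = 0.533, so -10 × [3.6/4.133]/0.9 = -9.68.
- Emax2: ED50 = 4.8 × 0.3/0.7 = 2.057, so -10 × [3.6/5.657]/0.7 = -9.09.
- Sigmoid Emax: ED50 = 2.4 and 2^h = 9, so h = 3.17 and the mean is -8.70.

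**Randomised 4.8 mg arm with k step-downs.** Arm mean = [(70 - k)(-10) + k × (mean at 3.6 mg)]/70. Success (%) for k = 10 is then interpolated in the protocol's own Table 7.5:1. For linear: 67.8 + (9.643 - 9.5)/0.5 × (82.8 - 67.8) = 72.1. The last two columns are from a direct simulation of the randomised-dose analysis.

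| Shape | Arm mean, k=10 | Arm mean, k=20 | Interpolated, k=10 | Simulated, k=10 | Simulated, k=20 |
|---|---|---|---|---|---|
| Linear | -9.64 | -9.29 | 72.1 | 74.1 | 64.6 |
| Exponential | -9.29 | -8.57 | 60.0 | 61.0 | 34.6 |
| Emax1 | -9.95 | -9.91 | 82.4 | 83.0 | 82.8 |
| Emax2 | -9.87 | -9.74 | 79.3 | 80.9 | 77.9 |
| Sigmoid Emax | -9.81 | -9.63 | 85.4 | 86.3 | 82.6 |
| Average | | | 75.8 | 77.1 | 68.5 |

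A second, separately coded simulation gives averages of 76.6% and 68.4%. The average drops below 80% at about 7 step-downs of 70. The interpolation is approximate because Table 7.5:1 scales the lower doses together with the top one.

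**Where the loss arises.** For k = 10 and 20, the flat null is rejected in 100.0% and 100.0% of runs, the responder criterion is met in 98.7% and 96.8%, and the target-dose criterion in 76.9% and 68.8%.

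**Dependence on the assumptions.** With a response halfway between the received and randomised dose, the averages are 80.8% and 76.9%, and 80% is crossed at about 13 step-downs. If stepped-down patients lose as much as those who stay on dose, or if -10% is already the mean of the whole randomised arm, the figure is 84.4%.

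**The other three rows of Table 7.5:2.** Their counts do not fix which patients moved where, so no primary-analysis figure is derived from them. They enlarge the 2.4 mg group, whereas the week-10 rule in Protocol 4.1.4 moves D to C, and C and B to A. Sending the group C step-downs to 0.6 mg instead gives 82.6, 83.5 and 82.3% in the actual-dose analysis, against 82.4, 83.7 and 82.2% printed. The passages should be reconciled, but the table does not move.

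**The case for a change.** The best case for acting is that Table 7.5:2 itself implies the unfavourable assumptions. Only the allocation ratio is said to change. The 60 patients left on 4.8 mg therefore keep a mean of -10%, and the 10 who moved take the 3.6 mg mean. Analysing those same patients as randomised gives about 77%. Section 7.5 also claims more than 80% for every shape at 70 per group, and under this reading linear and exponential fall short with 10 step-downs. Choosing a dose is a stated purpose of the trial.

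The omission is real, and the on-dose reading is plausible. It is not the only one. The primary effect is defined by randomised group, and the planning mean is stated for a dose group of 70, which fits the randomised arm equally well.

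The shortfall also rests largely on one shape: without exponential, the k = 10 average is (74.1 + 83.0 + 80.9 + 86.3)/4 = 81.1%. For exponential with 20 step-downs the true randomised-arm mean is -8.57. No dose then reaches 9 points under the primary estimand, so finding no target dose would be the correct answer, and more patients would not alter it. Part of the fall is a smaller true effect rather than too few patients.

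**Conclusion.** The concern identifies a sensitivity figure that was not printed, not a wrong number or rule. Table 7.5:2 is correct, its title and lead-in state its scope, and its closing sentence is limited to the scenarios run. For the primary analysis the average lies between about 77% (10 step-downs) or 68-69% (20) and 84.4%, depending on what -10% denotes and how stepped-down patients respond. Neither is settled by the documents. A reader can get close to the 10-patient figure, about 76%, from the printed rows of Table 7.5:1.

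No decision depends on the missing figure. Proof of concept is safe at about 100%, Protocol 7.1 excludes confirmatory testing, and SAP 7.4.1 has the phase 3 dose also weigh tolerability, safety and other information. A sentence saying which mean -10.0% is would be a courtesy to the reader. It would change no sample size, dosing, analysis or conclusion.
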